## ABBREVIATIONS AND DEFINITIONS OF TERMS

CECPS	Client Engagement in Child Protective Services
EI	Early Intervention
StimQ	Measure of Cognitive Stimulation Provided in the Home
SAHL	Short Assessment of Health Literacy
BSID-III	Bayley Scales of Infant and Toddler Development, Third Edition
PITEI	Philadelphia Infant Toddler Early Intervention
FN	Family Navigator
IFSP	Individualized Family Service Plan
ACE	Adverse Childhood Experiences
CRS	Co-Parenting Relationship Scale
FF	Family Foundations

## ABSTRACT

### Context:

Developmental delays are frequently encountered among young children but disproportionately affect impoverished minority children leading to disparities in early child development. To promote healthy child development and reduce disparities, the Individuals with Disabilities Education Act (IDEA) mandates early intervention (EI) services be made available to young children with identified delays. However, only half of at-risk children initiate and complete referrals for EI services. Research suggests this may be due to misperceptions about EI services and logistical barriers that impede participation. As a result, many at-risk children do not receive needed services to improve their development early in life. It is unknown what strategies are effective to promote follow through with EI services. Thus, there is a critical need to identify effective strategies to foster initiation and completion of EI services among at-risk children. In the absence of such knowledge, public health agencies lack understanding of effective strategies to assist families with obtaining EI services and may propagate existing health disparities. Our long-term goal is to develop effective strategies to promote child development and reduce disparities through the development of our Opening Doors to Early Intervention Program, a patient navigation intervention designed to facilitate follow through with EI referrals and services. One parent from currently enrolled parent-child dyads in the Main RCT, will be recruited to participate in the sub-study which entails answering questions about safety net program use prior to and during the current COVID-19 pandemic through the completion of a survey. A subset of the sub-study participants will also be asked to participate in an audio-recorded semi-structured telephone interview to identify their perceptions of program assistance and needs. To determine changes in use of services, we will analyze differences in the proportion with past year and current program use to determine changes in demand for individual program services during the COVID-19 pandemic. In a separate sub-study, up to 50 experts will be participating in the Delphi consensus process and parents that are enrolled in the Main RCT study will participate in a virtual focus group using a CHOP approved conferencing software, to adapt an evidence based co-parenting program for caregivers who have experienced childhood trauma.

### Objectives:

- 1) To test the effectiveness of the Opening Doors to Early Intervention Program on EI service use and child developmental status among poor minority children residing in an urban community.
  - 2) To develop a measure of engagement and assess whether parent engagement mediates the effects of the Opening Doors to Early Intervention Program.
-

- 
- 3) To explore whether the home learning environment, parental health literacy, or poverty moderate the effects of the Opening Doors to Early Intervention Program on child developmental status.
  - 4) To determine changes in use of and need for safety net programs and adjustment to a remote service delivery model for Early Intervention services among low-income families of children with developmental disabilities during the current COVID-19 pandemic in Philadelphia.
  - 5) To adapt an evidence-based co-parenting program for use among caregivers who have experienced significant trauma and chronic stress as a child.

**Study Design:**

The main study is a prospective, randomized comparative effectiveness trial to study the effects of a novel patient navigation strategy on the use of EI referrals and services and on child developmental outcomes among at-risk urban minority children. For the sub-study, a total of around 128 subjects, one parent from each of the currently enrolled parent-child dyads in the Main RCT, will be recruited to participate in the COVID-rapid response sub-study. A subset of around 50 participants will be enrolled into the sub-study, along with up to 50 experts (in the fields of parenting, childhood trauma, and/or co-parenting) to participate in focus groups and Delphi consensus process.

**Setting/Participants:**

In the randomized controlled trial, we plan to recruit 4-6 urban practices from CHOP's Pediatric Research Consortium (PeRC) to participate in the study. These practices care for a diverse, complex urban population and have onsite social workers to assist with family crises.

A total of 360 eligible children, 90 children/year, will be recruited from participating practices to achieve a diverse sample of children. Children will be eligible to participate if they are <30 months old, >35 weeks estimated gestational age, reside in Philadelphia, have parents who speak English or Spanish, and have recently been referred to the Philadelphia Infant Toddler Early Intervention Program in Philadelphia County. Children >30 months old will not be eligible, since they are transitioning to Preschool Early Intervention (Part B services) and have little time for retention or completion of the program. In addition, children outside of Philadelphia County will not be eligible, since they would be referred to EI services in a different county. Children will be excluded if they have received EI services in the past two weeks.

The COVID-19 Rapid Response sub-study will recruit around 128 subjects from the Main RCT, one parent from each of the currently enrolled parent-child dyads in the Main RCT. Subjects are eligible if they have participated, or are currently participating, in the Main RCT and have provided permission to be contacted for future studies.

The Childhood Trauma sub-study will recruit up to 50 experts in the fields of parenting, childhood trauma, and/or co-parenting to participate in a modified Delphi consensus process

---

concerning childhood trauma topics to include into an existing co-parenting primary program used nationally in childbirth educational settings. Then, up to 50 parents of subjects from the Main RCT to participate in a virtual interviews to provide feedback on the adapted co-parenting program.

To summarize, a total of 410 subjects are anticipated between the two subject groups designated for this study. The first group of subjects will include 360 participants for the Main RCT study, and these subjects will be recruited for the COVID-19 sub-study and also for Phase 2 of the Trauma-Informed Co-parenting Sub-study. The second group of subjects (Delphi Consensus group) will include up to 50 experts that will participate in Phase 1 of the Trauma-Informed Co-parenting Sub-study.

#### Study Interventions and Measures:

In the Main RCT, we will rigorously study the effects of the Opening Doors to Early Intervention Program's Family Navigator (FN) intervention on the use of EI referrals and services and on child developmental outcomes among at-risk urban minority children.

In the COVID-19 Rapid Response sub-study, we will survey participants concerning safety net program use prior to and during the current COVID-19 pandemic as well as current needs that are not addressed by program participation. . The survey will inquire about current and past year participation in the following safety net programs: unemployment benefits; Medicaid or Children's Health Insurance Program (CHIP); Women, Infants, and Children (WIC); Temporary Assistance to Needy Families (TANF); Supplemental Nutrition Assistance Program (SNAP); Supplemental Security Income (SSI); Early Head Start; and county Early Intervention services. Questions derived from the latest Survey of Income and Program Participation (SIPP) will be utilized to query participants on program use before and after the onset of the pandemic. To gain an in-depth understanding of safety net program use and adjustment to new service delivery models, we will conduct telephone interviews with 20-30 parents to identify their perceptions of program assistance and needs. We will inquire about each program they are currently participating in, how services are delivered (e.g. virtually), and whether the current format meets their needs. We will also inquire about barriers and facilitators to program participation and what unmet needs they currently have. An interview guide will be developed for the interviews. All interviews will be audiotaped and transcribed for analysis.

In the Childhood Trauma sub-study, we will conduct 3-5 rounds of a modified Delphi process with up to 50 experts (fields of parenting, childhood trauma, and/or co-parenting) to develop a consensus list of childhood trauma and stress topics for inclusion in an adapted co-parenting program known as Family Foundations (FF). We will then adapt the FF and conduct interviews with up to 50 parents of participating children who report 2 or more ACEs on their baseline survey from the main RCT, using a CHOP approved conferencing software. Parents in the interviews will provide feedback on the adapted program regarding

---

topics, feasibility, acceptability, and appropriateness. Focus groups will be led by research staff and will be audiotaped and transcribed for thematic analysis.

---

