## **2.2 Secondary Objectives (or Aim)**

Specific Aim 2: To assess whether parent engagement mediates the effects of the Opening Doors to Early Intervention Program.

Specific Aim 3: To explore whether the home learning environment, parental health literacy, adverse childhood experiences or poverty moderate the effects of the Opening Doors to Early Intervention Program on child developmental status.

- a. *Aim 3a:* To explore whether differences in developmental scores between intervention and control groups varies by the richness of home learning environments.
- b. *Aim 3b:* To explore whether differences in developmental scores between intervention and control groups varies by the health literacy level of parents.
- c. *Aim 3c:* To explore whether differences in developmental scores between intervention and control groups varies by family income level.

Specific Aim 4: To determine changes in use of and need for safety net programs and adjustment to a remote service delivery model for Early Intervention services among low-income families of children with developmental disabilities during the current COVID-19 pandemic in Philadelphia by way of the COVID-19 Rapid Response Sub-study.

Specific Aim 5: To adapt an already in use evidence-based co-parenting program used nationally in childbirth education settings, for use among caregivers who have experienced significant trauma and chronic stress as a child by way of the Trauma-Informed Co-parenting Sub-study.

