### **3.1.2 COVID-19 Rapid Response Sub-study: Safety Net Program Use Among Low-Income Families of Children with Developmental Disabilities During a Pandemic**

One parent from each of the currently enrolled parent-child dyads in the Main RCT will be contacted by telephone to obtain verbal consent for participation in this sub-study.

Participants consented into the sub-study will be surveyed concerning safety net program use prior to and during the current COVID-19 pandemic. We will also survey these participants concerning current needs that are not addressed by program participation. The survey will be conducted via RedCap at CHOP, which is the method currently used to collect study measures every 3 months. The survey will inquire about current and past year participation in the following safety net programs: unemployment benefits; Medicaid or Children's Health Insurance Program (CHIP); Women, Infants, and Children (WIC); Temporary Assistance to Needy Families (TANF); Supplemental Nutrition Assistance Program (SNAP); Supplemental Security Income (SSI); Early Head Start; and county early intervention services. Questions derived from the latest Survey of Income and Program Participation (SIPP) will be utilized to query participants on program use before and after the onset of the pandemic.

To gain an in-depth understanding of safety net program use, we will conduct telephone interviews with 20-30 parents to identify their perceptions of program assistance and needs. We will inquire about each program they are currently participating in, how services are delivered (e.g. virtually), and whether the current format meets their needs. We will also inquire about barriers and facilitators to program participation and what unmet needs they currently have. An interview guide will be developed for the interviews. All interviews will be audiotaped and transcribed for analysis.

---

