RedCap surveys will be exported to a Stata data file for cleaning and analysis. To determine changes in use of services, we will analyze differences in the proportion with past year and current program use to determine changes in demand for individual program services during the COVID-19 pandemic. We will model changes in service use by family income category, race/ethnicity, and education level. Interview transcripts will be analyzed using NVivo, a qualitative software program. Transcripts will be coded, and themes will be generated using a deductive consensus approach and Grounded Theory.

This sub-study will provide important information on current safety net program use and needs among low-income families of children with developmental disabilities during the current COVID-19 pandemic. This information can inform service needs and barriers to access to services for future pandemic planning, when needs are expected to increase due to employment furloughs and layoffs and access to services may be limited by social distancing policies.

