#### ***6.4.2.4 Specific Aim 4***

By way of the COVID-19 Rapid Response sub-study, we will determine changes in use of and need for safety net programs among low-income families of children with developmental disabilities during the current COVID-19 pandemic in Philadelphia.

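### Aim 4 promises change in need for safety net programs, but the survey as described asks about need only at present and reads change in use as change in demand

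*Protocol*

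**What the plan says.** **The aim.** Item 4 of the Objectives in the protocol Abstract reads "To determine changes in use of and need for safety net programs". Section 2.2 repeats it: "To determine changes in use of and need for safety net programs and adjustment to a remote service delivery model". Section 6.4.2.4, the statistical entry for Aim 4, says "we will determine changes in use of and need for safety net programs among low-income families of children with developmental disabilities" and names no need variable, comparison or model.

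**The data.** The Abstract (Study Interventions and Measures) says the survey covers "safety net program use prior to and during the current COVID-19 pandemic as well as current needs that are not addressed by program participation". Section 3.1.2 says the same of need: "We will also survey these participants concerning current needs that are not addressed by program participation". Participation in eight listed programs is asked for the past year and for now, and the before-and-after questions concern use. Interviews with 20-30 parents ask about delivery, barriers and present unmet needs. Section 4.2 lists one survey and one interview, with no repeat.

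**The analysis.** Section 3.1.2 will analyze "differences in the proportion with past year and current program use to determine changes in demand for individual program services". The Context paragraph of the Abstract states the same analysis. The planned modelling, by income, race/ethnicity and education, is also of change in service use. The SAP covers Aims 1 to 3 only.

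**The concern.** A change needs two measurements. Use has two and need has one, so the need part of the stated change has no estimator in the described data. The analysis fills the gap by treating change in use as change in demand. A family uses a program when it needs it and can obtain it, so change in use mixes change in need with change in access. If access fell while need rose, the two effects pull the use figure in opposite directions.

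Sections 3.1.2 and 9.4.3 say the results are to inform service needs and barriers for future pandemic planning. A reader who takes the use comparison as a measure of demand could conclude that need for a program rose less than it did or, in some conditions, that it did not rise.

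**Working it through.** The documents give no expected rate, effect size or precision for Aim 4, so there is no figure of the plan's own to reproduce. The check has two parts.

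**1. Aim, data and analysis side by side**

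| Quantity | Change promised? | Periods described | Change analysis described |
|---|---|---|---|
| Use of each program | Yes (Objectives item 4; 2.2; 6.4.2.4) | Past year and current | Difference in proportions; model of change in use |
| Need for programs | Yes (same places) | Current only, as unmet need | None; change in use is labelled change in demand |

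**2. How far change in use can stand in for change in need**

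Let n be the share of families who need a program and a the share of those in need who obtain it, with 1 for before and 2 for during. Assume that only families in need use the program, and that the two use measures are otherwise comparable.

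- Use = n × a
- Reported change = n2 × a2 - n1 × a1
- Unmet need = n × (1 - a)
- A rise in need shows as no change or a fall only if n2 × a2 ≤ n1 × a1, that is, if a2/a1 ≤ n1/n2

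The rates below are assumptions, since the documents give none. With n1 = 50% and a1 = 80%, use before is 0.50 × 0.80 = 40% and unmet need before is 0.50 × 0.20 = 10%.

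| Need during | Access during | Use during | Reported change (points) | Unmet need during |
|---|---|---|---|---|
| 60% | 80% | 48% | +8 | 12% |
| 60% | 75% | 45% | +5 | 15% |
| 60% | 70% | 42% | +2 | 18% |
| 60% | 66.7% | 40% | 0 | 20% |
| 60% | 60% | 36% | -4 | 24% |
| 60% | 50% | 30% | -10 | 30% |
| 70% | 80% | 56% | +16 | 14% |
| 70% | 70% | 49% | +9 | 21% |
| 70% | 60% | 42% | +2 | 28% |
| 70% | 57.1% | 40% | 0 | 30% |
| 70% | 50% | 35% | -5 | 35% |

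The break-even access ratios are 0.50/0.60 = 0.83 and 0.50/0.70 = 0.71. When access falls by less than that, the rise in need still appears as a rise in use, but a smaller one. In every row unmet need rises from 10%, but the described survey would capture only the later value.

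**The case against.** Four points can be made for the plan.

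- **The sentence can be parsed differently.** It could mean changes in use, and separately need. Section 3.1.2 also describes the output as current use and needs, which the survey delivers. This has some force, but Section 3.1.2 and the Abstract still claim changes in demand, which the use comparison does not measure.
- **Need is not hidden.** The survey asks about current unmet need, and the interviews cover barriers and delivery. This stands. A reader might infer that a program families could no longer reach would simply look unneeded, or that half of Aim 4 is lost. The documents do not support that: change in use, current need and adjustment to remote delivery (named in the Objectives and Section 2.2) can still be addressed. Only the change in need is missing.
- **A reversed sign is not a given.** A reader might infer that rising need would be reported as flat or falling demand. That requires access to fall at least in proportion to the rise in need, and the documents give no access figures. Section 3.1.2 does say "access to services may be limited by social distancing policies", but of future pandemic planning. It shows that need and access can diverge, not that access to these programs fell in the period surveyed.
- **The questionnaire is not in the documents.** A past-need item cannot be excluded. What can be said is that none is described and no analysis of one is planned.

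**Conclusion.** The point holds in limited form. As described, the sub-study cannot estimate change in need, and its use comparison does not support a statement about change in demand.

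The size of the error depends on access, which is unknown. If access was unchanged, use moves in proportion to need. If access fell, a rise in need is understated. Under the assumed rise from 50% to 60%, the reported change runs from +8 points with access unchanged at 80% to -10 points at 50%, crossing zero at 66.7%. The illustration assumes that only families in need use a program and that past-year and current use are otherwise comparable. The first part of the finding, that change in need has no estimator, needs neither assumption.

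This concerns a stated secondary aim in a sub-study of about 128 parents (Section 3.3.2). The main RCT primary endpoint is not affected.

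**What to change.** **Wording change, sufficient by itself.** In Objectives item 4, Section 2.2 and Section 6.4.2.4, restrict the aim to *changes in use of, and current unmet need for,* the programs. Replace *changes in demand* by *changes in use* both in the Context paragraph of the Abstract and in Section 3.1.2; changing only one leaves the protocol inconsistent. This costs a text edit and brings the aim into line with the output that Section 3.1.2 already describes.

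**Alternative, if the survey can still be changed.** For each of the eight listed programs, add a needed-but-not-received item for the pre-pandemic and the current period, using the same recall windows as the use items. That is at most 8 × 2 = 16 items. Need in each period is then use plus needed-but-not-received. Report paired changes in need and in unmet need separately from change in use, and add this analysis to Section 6.4.2.4. The cost is a longer survey and reliance on recalled need, which is more subjective than recalled enrolment.

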**TABLE 1: SCHEDULE OF STUDY PROCEDURES**

Study Phase	PreStudy Visit	Screening/ Study Visit 1 (Baseline)	Follow-up Study Visits			
Measure			V2 (3 mo)	V3 (6 mo)	V4 (9mo)	V5 (12 mo)
Informed Consent		X				
Review Inclusion/ Exclusion Criteria		X				
Demographics		X				
*SAHL		X	(X)	(X)	(X)	(X)
StimQ		X				
Poverty		X				
EI Engagement		X	X	X	X	X
EI Referral			X	X	X	X
EI Services			X	X	X	X
*Phila Exp. ACE			X	(X)	(X)	(X)
*Public Policy			X	X	X	X
*BSID-III						X

\*Philadelphia Expanded ACEs measure is administered only once throughout the duration of the study, during the 3-month follow-up survey. However, this measure may be completed during a later time-point in the event that it is not completed during the 3-month time-point.

\*Due to the interactive nature of the SAHL measure, in the event that the baseline visit must be conducted remotely, the participant will have the option of either completing the SAHL by utilizing a video conferencing application or completing the SAHL in-person at a later date. As a result, the SAHL is a baseline measure that may be completed during a subsequent follow-up visit. If a visit is conducted using a video conferencing application, we will try to use a HIPAA-compliant application licensed by CHOP (i.e., Skype, Bluejeans or WebEx).

\*Public policy changes that may impact access to services (e.g. changes in EI funding or eligibility) will be queried of EI staff throughout the study period.

\*BSID-III: In the event in-person procedures cannot take place at the time of the final study visit time-point (due to COVID-19 or other reasons) this assessment may be performed beyond the 12-month time-point, at a later date, any time before the child turns 42 months and 15 days old.

